13.2. Assessing Adverse Events

In conjunction with the medical monitor, the Investigator will evaluate adverse events to ensure the events are categorized correctly. Elements of categorization will include:

- Seriousness/Classifications (see definition in Section 13.1)
- Causality or Relatedness – i.e. the relationship between the test article, study treatment or study procedures and the adverse event (not related; unlikely related; possibly related; related - see definition in Section 13.2.1)
- Adverse Event Severity – Adverse event severity is used to assess the degree of intensity of the adverse event (mild; moderate; severe for all events - see definition in Section 13.2.2)
- Outcome – not recovered or not resolved; recovering or resolving; recovered or resolved with sequelae; recovered or resolved; death related to adverse event; unknown
- Actions Taken – none; temporarily discontinued; permanently discontinued; other

13.2.1. Causality Assessment

Causality Assessment – A determination of the relationship between an adverse event and the test article. The test article relationship for each adverse event should be determined by the investigator using these explanations:

- Not Related- An adverse event that is not related to the use of the test article, study treatment or study procedures
- Unlikely Related – An adverse event for which an alternative explanation is more likely, e.g. concomitant treatment, concomitant disease(s), or the relationship of time suggests that a causal relationship is not likely
- Possibly Related – An adverse event that might be due to the use of the test article, or to the study treatment or study procedures. An alternative explanation, e.g. concomitant treatment, concomitant disease(s), is inconclusive. The relationship in time is reasonable. Therefore, the causal relationship cannot be excluded
- Related – An adverse event that is listed as a possible adverse effect (device) or adverse reaction (drug) and cannot be reasonably explained by an alternative explanation, e.g. concomitant treatment of concomitant disease(s). The relationship in time is very suggestive, e.g. it is confirmed by de-challenge and re-challenge

13.2.2. Severity Assessment

Severity Assessment – A qualitative assessment of the degree of intensity of an adverse event as determined by the Investigator or reported to him/her by the subject. The assessment of severity is made irrespective of test article, study treatment or study procedure relationship or seriousness of the event and should be evaluated according to the following scale:

- Mild – Event is noticeable to the subject, but is easily tolerated and does not interfere with the subject's daily activities
- Moderate – Event is bothersome, possible requiring additional therapy, and may interfere with the subject's daily activities
- Severe – Event is intolerable, necessitates additional therapy or alteration of therapy and interferes with the subject's daily activities

13.3. Documentation and Follow-Up of Adverse Events

The recording and documenting of adverse events (ocular and non-ocular) begins when the subjects are exposed to the test article, study treatment or study procedure. Adverse events reported before the use of test article, start of study treatment, or study procedures will be recorded as medical history. However, if the condition deteriorates at any time during the study it will be recorded and reported as an AE. Untoward medical events reported after the subject's exit from the study will be recorded as adverse events at the discretion of the Investigator.

Upon finding an adverse event, the Principal Investigator will document the condition in the subject record and in the eCRFs. He/she will complete the Adverse Event /eCRF.

Complete descriptions of all adverse events must be available in the subject record. All Adverse Events including local and systemic reactions not meeting the criteria for "serious adverse events" shall be captured on the appropriate case report form or electronic data system. All adverse events occurring while the subject is enrolled in the study must be documented appropriately regardless of relationship.

It is the Investigator's responsibility to maintain documentation of each reported adverse event. All adverse events will be followed in accordance with applicable licensing requirements. Such documentation will include the following:

- Adverse event (diagnosis not symptom)
- Drawings or photographs (where appropriate) that detail the finding (e.g., size, location, and depth, etc.)
- Date the clinical site was notified
- Date and time of onset
- Date and time of resolution
- Adverse event classification, severity, and relationship to test articles, as applicable
- Treatment regimen instituted, including concomitant medications prescribed, in accordance with applicable licensing requirements
- Any referral to another health care provider if needed
- Outcome, ocular damage (if any)

- Likely etiology
- Best corrected visual acuity at the discovery of the event and upon conclusion of the event

In addition, if an infiltrate(s) is present, he/she will complete the Corneal Infiltrate Assessment eCRF. Where necessary, a culture of the corneal lesion will be collected to determine if the infection is microbial in nature. If cultures are collected, the date of culture collection and laboratory utilized will be recorded.

Changes in the severity of an AE shall be documented to allow an assessment of the duration of the event at each level of intensity to be performed. Adverse events characterized as intermittent require documentation of the onset and duration of each episode. Changes in the assessment of relationship to the Test Article shall also be clearly documented.

Subjects who present with an adverse event shall be followed by the Investigator, within licensure, until all signs and symptoms have returned to pre-treatment status, stabilized, or been satisfactorily resolved. If further treatment beyond licensure is required, the patient will be referred to the appropriate health care provider. The Investigator will use his/her clinical judgment as to whether a subject reporting with an adverse event will continue in the study. If a subject is discontinued from the study, it will be the responsibility of the Investigator to record the reason for discontinuation. The Investigator will also document the adverse event appropriately and complete the Adverse Event eCRF. Any subjects with ongoing adverse events related to the test article, study treatment or study procedures, as of the final study visit date, should be followed to resolution of the adverse event or until referral to an appropriate health care provider, as recommended by the Investigator. Non-ocular adverse events that are not related to the test article, study treatment, or study procedures may be recorded as "ongoing" without further follow-up.

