1.4. Summary of Known Risks and Benefits to Human Subjects

The following risks/adverse events can be associated with wearing soft contact lenses in general:

- There may be less comfort than when the lens was first placed on the eye.
- The eyes may burn, sting and/or itch.
- There may be a feeling of something in the eye (foreign body, scratched area).
- There may be the potential for some temporary impairment due to peripheral infiltrates, peripheral corneal ulcers and corneal erosion.
- There may be the potential for other physiological observations, such as local or generalized edema, corneal neovascularization, corneal staining, injection, tarsal abnormalities, iritis and conjunctivitis, some of which are clinically acceptable in low amounts.
- There may be excessive watering, unusual eye secretions, or redness of the eye.
- Poor visual acuity, blurred vision, rainbows or halos around objects, photo-phobia, or dry eyes may also occur if the lenses are worn continuously or for too long a time.

There is no direct benefit to the subject for participating in the study, although they will be able to try out contact lenses and contact lens care products. The information from this study will aid in the further development and design of new contact lenses.

For the most comprehensive clinical information regarding the contact lenses and care products refer to the package inserts (Appendix C).

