Visit 2 (Baseline/Fitting/45 min Follow-up): Modified CLDEQ-8, slit-lamp eligibility, fitting of lens pair #1 (Insertion, ocular symptoms, VAS comfort rating, visual acuity, lens fit, surface characteristics). 45 minutes of lens wear. Follow-up on lens pair #1 (ocular symptoms, VAS comfort rating, visual acuity, lens fit, surface characteristics, slit-lamp).

Washout (subject wears 1-DAY ACUVUE® MOIST) 5-7 days

Visit 3 (Fitting/120 min Follow-up/Washout): Modified CLDEQ-8, slit-lamp eligibility, fitting of lens pair #2 (Insertion, ocular symptoms, VAS comfort rating, visual acuity, lens fit, surface characteristics). 120 minutes of lens wear. Follow-up on lens pair #2 (ocular symptoms, VAS comfort rating, visual acuity, lens fit, surface characteristics, slit-lamp).

Washout (subject wears 1-DAY ACUVUE® MOIST) 5-7 days

Period 2: Solution 1 and Solution 3 soaked lenses

Visit 4 (Baseline/Fitting/45 min follow-up): Modified CLDEQ-8, slit-lamp eligibility/fitting of lens pair #3 (Insertion, ocular symptoms, VAS comfort rating, visual acuity, lens fit, surface characteristics). 45 minutes of lens wear/Follow-up on lens pair #3 (ocular symptoms, VAS comfort rating, visual acuity, lens fit, surface characteristics, slit-lamp).

Visit 5 (Fitting/120 min Follow-up): Modified CLDEQ-8, slit-lamp eligibility, fitting of lens pair #4 (Insertion, ocular symptoms, VAS comfort rating, visual acuity, lens fit, surface characteristics). 120 minutes of lens wear. Follow-up on lens pair #4 (ocular symptoms, VAS comfort rating, visual acuity, lens fit, surface characteristics, slit-lamp). Final evaluation.

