4.3. Enrollment Target and Study Duration

A total of up to 120 subjects (i.e. 40 per study lens) will be enrolled (informed consent signed). The goal is for a sample size of approximately 90 subjects (i.e. 30 per study lens) after subjects who withdraw or are lost to follow-up.

The Investigator is responsible for ensuring that all subjects entering the study conform to subject selection criteria. The number of subjects targeted for randomization and completion are as follows:

The number of subjects targeted for randomization and completion are as follows:

Table 1: Target number of subjects by arm and site

	ACUVUE 2	OASYS	Vita	Total
Randomization	36	36	36	108
Completion	30	30	30	90
Number of sites				4
Number of subjects/site	25-35	25-35	25-35	90-120
Min-Max				

The study will last approximately four weeks for each subject and the entire study duration will be approximately 4 months and include a 2-month enrollment period.

Once the informed consent has been signed the subject will be considered enrolled.

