2.29.	Dispense	
The washout lenses, 1-DAY ACUVUE® MOIST will be dispensed for a 5-7 day wearing period
 
 • Dispense enough lenses to last the subject to their scheduled follow-up visit. Do not dispense extras*. • The lenses will be dispensed with right and left eye designation. • The lenses will be worn as daily disposable only. • Study approved rewetting drops are permitted if needed. • No other contact lenses should be worn during the wear period (spectacles may be worn) • No solutions or care products should be used • Subjects may use reading glasses over study contact lenses as needed • A patient instruction guide will be provided. • Subjects will be scheduled for Visit 2 in approximately 5-7 days. 
* Note: In the event a lens is lost or damaged, the subject will return to the clinical site for replacement. As much as reasonably possible, a damaged lens and packaging should be returned to the clinical site (wet, if possible) and then returned to the Sponsor. If lens damage is present, complete the Product Quality Complaint Form, if applicable. The lens will be stored in labeled vial with study provided solution, and clearly differentiated from the other worn lenses that will be shipped back to the Sponsor.

Prior to Visit 3, randomized lenses will be prepared.

Sixteen to twenty-eight hours prior to Visit 3, the subject's lenses will be soaked in the test solutions in the sponsor provided lens cases. (See work aid for lens preparation instructions)

VISIT 3

The subjects must present to Visit 3 wearing their habitual spectacles (if applicable) having not worn contact lenses the day of the visit.

Visit 3: Confirm Baseline		
Step	Procedure	Details
3.1.	Adverse Events and Concomitant Medications Review	Review any changes to the subject's medical history or concomitant medications from the previous study visit. Record any changes, and any adverse events.
3.2.	Compliance	Confirm compliance with the dispensed Washout lenses.
3.3.	Subject Reported Ocular Symptoms	Subjects will respond to a verbal open-ended symptoms questionnaire.
3.4.	Follow-Up modified CLDEQ-8 Questionnaires	The subject will respond to the Follow-Up modified CLDEQ-8 Questionnaires. Note: instruct the patient to think about how their wash-out contact lenses feel on an average day and answer the questions based on this level of comfort.

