5.24.	Subjective Lens Fit Assessment	
Evaluate overall lens fit acceptance (acceptable or unacceptable) based on centration, movement and other fitting characteristics.
 
An unacceptable fit is deemed by one of the following criteria:
 
 • limbal exposure at primary gaze or with extreme eye movement • edge lift • excessive movement in primary and up gaze • insufficient movement in all three of the following conditions: primary gaze, up gaze, and Josephson push up 
Note: if lens fit is unacceptable subject will be discontinued from the study.

5.25.	White Light Lens Surface Wettability	Record the white light lens wettability of both lenses.
5.26.	Surface Deposits	Record any front and back surface lens deposits.
5.27.	Remove lenses	Lenses will be removed and discarded
5.28.	Slit Lamp Biomicroscopy	
FDA Slit Lamp Classification Scale will be used to grade the findings and determine eligibility.
 
Any adverse events must be followed to resolution.
 
Note 1: The following [REDACTED] will be used to assess specific ocular physiology in greater detail:
 
 • [REDACTED] Limbal and conjunctival redness • [REDACTED] Expanded Corneal staining • [REDACTED] Conjunctival staining 
Note 2: Each eye should be photo-documented if significant (Grade 2 or more) fluorescein corneal staining noted.

Visit 5: Lens Pau # 4 Follow-Up			
Step	Procedure	Details	
		If the clearance of the fluorescein needs to be expedited, preservative-free rewetting drops or saline may be instilled.	

FINAL EVALUATION

The final evaluation will ordinarily take place immediately following the last scheduled follow-up visit per the study protocol. It may also take place at any point the subject discontinues the study or is terminated from the study.

Final Evaluation			
Step	Procedure	Details	
F.1	Final Exam Form	Indicate if the subject completed the study successfully. If subject discontinued from the study indicate the reason.	
F.2	Exit Distance Visual Acuity	Record the exit distance visual acuity OD, OS, OU with the subject's spectacles or the same method used in Baseline entrance distance visual acuity.	

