14.2. Sample Size Justification

This is a pilot study and the sample size was not based on any empirical power calculation. The collected data will be used to design future clinical evaluation.

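### Ocular events first reported after the last 2-hour exposure are mostly left to the investigator's discretion, while the three earlier exposures each get a required review 5-7 days later

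*Combined protocol and SAP*

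**What the plan says.** Section 4.1 and Table 5 give each subject four in-office exposures to soaked lenses: 45 minutes at Visits 2 and 4, and 120 minutes at Visits 3 and 5 ("Visit 3 (Fitting/120 min Follow-up/Washout" and "Visit 5 (Fitting/120 min Follow-up"). Visits 3, 4 and 5 each fall 5-7 days after the visit before.

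In Section 7.2, each of those three visits opens with the same instruction (steps 3.1, 4.1, 5.1): "Review any changes to the subject's medical history or concomitant medications from the previous study visit. Record any changes, and any adverse events". A slit lamp examination with staining follows before the next lens goes in (steps 3.6, 4.6, 5.6).

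After the Visit 5 exposure the protocol asks for comfort, symptoms, acuity, fit and surface checks, lens removal, and then a slit lamp with corneal and conjunctival staining (step 5.28). After that, "The final evaluation will ordinarily take place immediately following the last scheduled follow-up visit per the study protocol". The Final Evaluation has two items: a completion form and exit acuity. Section 7.2 schedules no later visit, call or message.

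Section 13.3 makes recording of adverse events mandatory during enrolment. For events reported later it changes the rule: those reported after a subject's "exit from the study will be recorded as adverse events at the discretion of the Investigator". The clause makes no exception for ocular, related or serious events and sets no time limit.

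Section 1.4 lists, among the risks of soft lens wear, "temporary impairment due to peripheral infiltrates, peripheral corneal ulcers and corneal erosion". Ocular adverse events are a listed study endpoint, and Section 14.1 has safety variables summarised by solution and lens type.

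**The concern.** The same event is treated differently depending on the visit that preceded it. An ocular event that a subject reports the day after Visit 3 must be recorded. The same event reported the day after Visit 5 is, in most cases, recorded only if the investigator decides to do so. Both follow a 120-minute exposure, the longest wear studied.

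Two things are at stake. Delayed ocular events after the last exposure may be under-recorded, so event counts per exposure could be too low. And with four sites and no criterion for using the discretion, sites may count late events differently. The study is a pilot whose data are meant to inform later evaluations (Section 14.2), so uneven capture could carry forward into planning.

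**Working it through.** The plan states no figure for adverse-event follow-up, so there is none to reproduce. The check is a count over the visit schedule.

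**Inputs**
- Exposure times and visit spacing: Section 4.1 and Table 5.
- Completers: 90, from Section 4.3 ("The goal is for a sample size of approximately 90 subjects (i.e. 30 per study lens").
- Randomised: 108, from Table 1.
- Sample size basis: "This is a pilot study and the sample size was not based on any empirical power calculation" (Section 14.2), so no error rate or margin enters.

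**Schedule side by side**

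| Exposure | Minutes | Same-day exit slit lamp | Required AE review and slit lamp 5-7 days later |
|---|---|---|---|
| Visit 2 | 45 | yes | yes (Visit 3) |
| Visit 3 | 120 | yes | yes (Visit 4) |
| Visit 4 | 45 | yes | yes (Visit 5) |
| Visit 5 | 120 | yes | none |

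**Share of exposures without the later review, per completer**
- Two-hour exposures: 1/2 = 50%.
- All exposures: 1/4 = 25%.
- Minutes of soaked-lens wear: 120/(45 + 120 + 45 + 120) = 120/330 = 36.4%.

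**Counts**
- 90 completers: 90 of 2 x 90 = 180 two-hour exposures, and 90 of 4 x 90 = 360 exposures overall.
- 108 randomised, no drop-out: 108 of 216 two-hour exposures.

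**Sensitivity to drop-out.** Assume that 108 are exposed at Visit 3, 90 at Visit 5, and all 18 losses fall between. There are then 108 + 90 = 198 two-hour exposures.
- All 18 return for the Visit 4 review: 90/198 = 45.5% lack a later review.
- All 18 leave at Visit 3: (90 + 18)/198 = 54.5%.

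So half is exact for completers and roughly right with the planned losses.

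**Is test versus control affected?** Assume equal sequences among the 90 completers, 45 each. Visit 5 then carries 45 CLEAR CARE eyes (Sequence 1), 45 OPTI-FREE eyes (Sequence 2) and 90 RevitaLens eyes.
- Each control: 45 of 90 two-hour eye-exposures lack the window, 50%.
- RevitaLens: 90 of 180, also 50%.

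The share is the same for all three solutions, and within Visit 5 both eyes of a subject lose the same window.

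**What active contact would add.** Suppose no delayed event is seen after 2-hour wear. The one-sided 95% upper bound on the event rate is 1 - 0.05^(1/n), treating a subject's two exposures as independent.
- n = 90 (Visit 3 only): 3.27%. n = 180 (with a contact after Visit 5): 1.65%.
- Per control pairing, equal sequences: 6.44% at n = 45, falling to 3.27% at n = 90.

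This gain belongs to a scheduled contact. A recording rule alone does not deliver it, because it depends on subjects coming forward.

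**The case against.** A reader might infer that the last exposure has no follow-up at all. It does have some: symptoms are asked about, the eyes are examined with staining after lens removal, and staining of Grade 2 or more is photographed. Events found then must be followed to resolution, and Section 13.3 has related events still ongoing at the final visit followed to resolution or referral. The gap covers only what begins, or is first reported, after exit.

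A reader might also infer that anything reported after exit is recorded only if the investigator chooses. That goes too far as well. Section 13.4.1 requires an unanticipated device effect to be reported within 24 hours of the investigator learning of it. Section 12 requires product complaints, including allegations about safety, to be logged within 24 hours and assessed for adverse-event status. Neither has a stated cut-off at exit. An event with onset before exit but reported later is arguably still covered by the duty to document events during enrolment.

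Further, the 5-7 day interval was set as a washout against carry-over (Section 4.2), not as a safety window. Subjects wear 1-DAY ACUVUE MOIST during it and may use rewetting drops, so events found at the next visit cannot be attributed to the soaked lens alone. Section 1.4 gives no onset times and the documents give no event rates, so missed events are possible but not shown. The products are marketed, the study is an exploratory pilot, comfort is the primary endpoint, and Section 14.7 leaves analysis of ocular adverse events to the responsible clinician's discretion. The Patient Instruction Guide is supplied separately and may already ask subjects to report symptoms.

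All of this limits the size of the point. It does not remove the discretionary clause, which still covers ocular events that start after exit and are neither unanticipated device effects nor complaints. Whatever the guide tells subjects, it would not change what the site must record.

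**Conclusion.** The concern holds as a limited gap in recording. Three of four exposures get a required review and slit lamp 5-7 days later. The fourth, half of the 2-hour exposures and a quarter of all exposures among completers, gets same-day checks only, and most events that come to light afterwards are recorded at the investigator's discretion. Delayed ocular events may therefore be under-recorded and recorded unevenly by site. How many cannot be estimated from the documents.

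A reader might infer that the gap biases the test solution against the controls. The documents do not support that: the two eyes lose the same window, and the randomised sequences balance which control falls at Visit 5. The primary comfort analysis is untouched.

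The 50% and 25% assume completers; under the assumed drop-out patterns the 2-hour share runs from 45.5% to 54.5%. The change is worth making because it is cheap and replaces a stated rule that treats like events unlike, but the study does not stand or fall on it.

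**What to change.** In Section 13.3, remove the discretion for ocular events. Any ocular event with onset within 7 days after the last soaked-lens exposure that becomes known to the site is recorded and reported as an adverse event, with a note of the lenses and solutions used since exit. Seven days is the upper end of the trial's own between-visit interval. At the Final Evaluation, add an instruction that subjects report ocular symptoms in that window to the site.

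This makes recording uniform across visits and sites, but it remains passive and does not equalise ascertainment with Visits 2 to 4. A brief scripted phone or message contact at 5-7 days would make it active; for a pilot of this kind it is optional.

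The cost is one sentence in Section 13.3 and one line in the Final Evaluation. The database stays open up to 7 days longer after the last Visit 5, and a few more events may be reported. Lens and solution use after exit is uncontrolled, so attribution of these events will be weaker than for those found during the washouts.
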